Outcome measures Primary outcome: Difference between MLP and KTFS in the change in interpalpebral fissure during and spontaneous blinking

Secondary outcome: Difference between MLP and KTFS in the changes in interpalpebral fissure during opening and volitional blinking

Secondary outcome: Proportion of subjects selecting each device at the end of the crossover

Population: Individuals with severe unilateral or bilateral ptosis defined as occlusion of the visual axis by the lid in the resting state

[figure not shown]
Phase: N/A

Clinical Trial to improve the magnetic levator prosthesis (MLP) including the development and testing of a novel adjustable force system and comparison to the Kinesio Tape frontalis sling (KTFS) Version 1

Number of Sites enrolling participants:	1
Description of Study Agent :	Magnetic levator prosthesis (MLP) with compatible spectacle frames
Study Duration:	Kinesio Tape frontalis sling (KTFS)
Participant Duration:	2 to 3 years
	8 or 9 weeks from enrollment to the end of the crossover period of the clinical trial, with an additional 8 weeks after the end of the crossover for subjects who have a clinical decision to participate in the extended wear part of the clinical trial

SCHEMATIC OF STUDY DESIGN

Also, please refer to the study schema:

FU: Follow up

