5 STUDY RECRUITMENT, ENROLLMENT AND WITHDRAWAL

Patient Gateway for recruitment will be utilized.

5.1 Participant Inclusion Criteria:

1. Presence of Blepharoptosis for at least one eye which occludes the visual axis in the resting state (no frontalis drive),
2. Moderate cognitive function or better defined as greater than or equal to 18 out of 30 on a pre-screening of the Mini-Mental State Exam.

3. Age 5 or older. (Children need to be included because they represent an important target population (pediatric neuro-muscular conditions), and because facial structure and skin characteristics may result in a different response than adults)

5.2 Participant Exclusion Criteria:

1. Absence of ptosis which occludes the visual axis
2. Presence of a corneal ulcer of any size, unless managed with a protective contact lens or other method and permission is granted from the candidate's managing eye doctor.
3. Age less than 5,
4. Severe Cognitive impairment defined as MMSE score <18, behaviors consistent with delirium (combinations of disorientation, hallucinations, delusions, and incoherent speech), or lethargy.
5. Presence of corneal hypoesthesia unless cleared for enrollment by a cornea or contact lens specialist;
6. Orbicularis weakness on the side of the ptosis.
7. Mechanical ptosis, including ptosis due to orbital or lid tumor, cicatricial processes affecting the movements of the upper lid, and exophthalmos.
8. Previous ptosis surgery less than 3 months prior to Visit 1.
9. Lid position affected by lid or conjunctival scarring.
10. History of herpes keratitis.
11. Periocular neurotoxin (eg, Botox, Xeomin, Dysport, Myobloc) injections on the side of the ptosis within 3 months prior to Visit 1 and during the study.
12. History of hyperthyroidism or thyroid eye disease (ie, exophthalmos, upper eyelid retraction, diplopia secondary to extraocular muscle involvement). Hypothyroidism that is controlled on medication is allowed.

Hypoesthesia and chronic corneal ulcers may be treated successfully, usually with artificial tears and/or a protective contact lens. Therefore, when there is hypoesthesia or chronic epithelial defect the PI will contact the candidate's cornea or contact lens specialist (e.g. via email or EMR message (EPIC)), and request permission to enroll the candidate. If they do not have a cornea or contact lens specialist, a consult with one at MEE who is not affiliated with the study will be requested prior to enrollment.

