7.3.2 CROSSOVER

After consent and enrollment, subjects will be randomly assigned to one of the two arms for the crossover period. In one arm subjects will receive the MLP first and the KTFS second. In the other arm, subjects will receive the KTFS first and the MLP second.

Each period of the crossover will last for about three weeks, including about two weeks of training in how to apply and remove the device followed by about one week of using the device at home. Training will be conducted at study visits at Mass Eye and Ear. Typically there will be two training visits. Baseline measures of eye lid blinking without and with the device will be taken during training. For the MLP, two baseline measures of eye lid blinking will be recorded one with the real MLP device and one with a sham MLP device to determine how much improvement might occur simply through a placebo effect. However, for the KTFS it will not be possible to take a baseline measure with a sham KTFS. Only subjects and caregivers who demonstrate sufficient ability to apply and remove the device will be permitted to take it home. During the period of home wear, there will be a video call every other day to monitor the subject’s use of the device and safety. During the kfts arm, an occupational or physical therapist consulting with the Massachusetts eye and ear study team may talk with the subject during the video conference call to ensure that the kinesio tape is in the correct position. Mass General Brigham approved software will be used for video calls. During the trial week of home use of devices, subjects will

also receive REDCap survey link notifications each day to complete a brief survey to log if they are wearing the device (see the detailed plan above, and see attached document for survey language and questions).

To ensure no carry-over effects, there will be a washout of about 2 weeks duration between the first and second period of the crossover during which subjects will not be permitted to use any device for their blepharoptosis. (This will be similar to their habitual state before enrollment since none of the participants would have been using any device for their blepharoptosis about two weeks before enrollment).

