10.2 Statistical Hypotheses

Primary outcome measure:

Statistics for the participant characteristics will be presented in terms of mean \pm standard deviation or median \pm interquartile range (25th to 75th). Within subjects repeated measurements, linear mixed effects regression will be used to determine the effect of treatment condition on the IPF values (spontaneous and resting state open), with a random intercept for the subject factor. Subject age, gender, blink sequence (the order of the blink recorded in the video), and the order of interventions (whether evaluated in the first or the second arm of the crossover) will be covariates of interest. Effect of each covariate will be investigated alone, and only statistically significant ($P < .05$) covariates will be included in the final regression model, from which, the estimated marginal means and their 95% confidence interval (CIs) will be reported for each of the outcomes. Missing values at the T2 time point will be imputed from another time point within the same subject (T1 by default or T0 if both T1 and T2 were not available). For volitional blinks, a test of proportionality will be performed to determine the effect of the 3 treatments on the probability of eye not fully closing.

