10.4.2 Analysis of the Primary Efficacy Endpoint(s)

We will use a repeated measures mixed effects model for analysis of the primary outcome measure (change in interpalpebral fissure during opening and spontaneous blinking). The model will include a random subject-level intercept and a fixed treatment effect (MLP or KTFS). A repeated measures model will be used with primary timepoint for analysis being after 1 week of use. . The model will also include fixed effects of treatment order (i.e., MLP: KTFS vs KTFS:MLP), and crossover period (period 1 or 2), and will control for age and sham opening interpalpebral fissure.

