10.4.9 Multiple Comparison/Multiplicity

P-values used to indicate significance will be corrected where appropriate. There is no plan for multiple comparisons.

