As a backup plan in case scheduling constraints mean that it is not possible to schedule a taping visit with the PT:

1. The PI will perform the tape placement.
2. The PI or the research staff will be in attendance as the participants practice placing the tape.
3. The entire process will be recorded and the video loaded onto a secure server or shared via Institutional DropBox
4. The PT will be responsible for reviewing the videos within two days of placement, to ensure proper technique.

Randomization

Participants will be assigned to one of two possible treatment allocations: 1) MLP then KTFS or 2) KTFS then MLP. The allocation will be performed using software that implements the process of minimization. The first participant will be assigned randomly with each subsequent participant assigned in such a way as to approximately balance the number of participants who are 65 years of age and over and who have acute vs chronic ptosis. We propose to balance for these two factors because adults over the age of 65 typically have thinner and looser eyelid skin, and participants with acute ptosis may recover while enrolled in the study, which may affect outcomes. Letter codes, randomly assigned to each of the treatment allocations by a researcher external to the study will be used by the software. The code breaker will be kept in a sealed envelope in a location known only to the external researcher. Data provided to the masked data assessors and the masked person conducting statistical analyses will use the letter codes to identify treatment allocation.

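### The eye-closure test for volitional blinks covers three conditions, so a significant result need not mean that MLP and KTFS differ, and no MLP-KTFS contrast on closure is specified

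*Combined protocol and SAP*

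**What the plan says.** Section 10.2 sets out the mixed model for fissure width and then adds, for volitional blinks, that "a test of proportionality will be performed to determine the effect of the 3 treatments on the probability of eye not fully closing". It does not name the third treatment, the type of test, the timepoint or any follow-up contrast.

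Elsewhere the comparison has two treatments:

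- The Protocol Summary gives the volitional-blink secondary outcome as "Difference between MLP and KTFS in the changes in interpalpebral fissure during opening and volitional blinking".
- Section 10.6.1 randomises two sequences of the same two devices: "Participants will be assigned to one of two possible treatment allocations: 1) MLP then KTFS or 2) KTFS then MLP".
- The model in Section 10.4.2 has "a fixed treatment effect (MLP or KTFS") as its treatment term. Section 10.4.3 applies that approach to volitional blinking, but to the change in fissure.

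Section 7.3.2 describes the only other recording conditions: "Baseline measures of eye lid blinking without and with the device will be taken during training", and in the MLP period two recordings, "one with the real MLP device and one with a sham MLP device". Section 10.4.9 says that P values will be corrected where that is appropriate, and then: "There is no plan for multiple comparisons".

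**The concern.** An overall test of three conditions has the null that MLP, KTFS and the third condition share one probability of incomplete closure. The trial asks whether MLP and KTFS differ. Rejecting the first null does not answer the second question.

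A difference confined to the third condition is plausible. Section 5.1 requires "Presence of Blepharoptosis for at least one eye which occludes the visual axis in the resting state", and Section 5.2 excludes orbicularis weakness. With no device, or with a sham that lifts little, one would expect the eye to close fully more often than with something holding the lid up. The logical gap does not depend on that direction, because any departure of the third condition can drive the result.

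Closure matters to the trial's argument. Section 2.1 faults skin tape for harm to the ocular surface when the eye does not close, and presents the magnet as a force that the orbicularis can overcome. A significant three-way P value could be taken as support for that claimed advantage even if the two devices close equally well.

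**Working it through.** **Inputs.** The documents give no closure rates, number of blinks or power for this test, so there is no planned figure to reproduce. I take 16 participants from Section 10.5, where that number is set for the primary outcome, and a 0.05 significance level. All closure rates below are assumptions.

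**Step 1: hand example.** Suppose the eye fails to close in 8/16 with MLP, 8/16 with KTFS and 1/16 in the third condition.

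- Pooled total: 17 of 48. Expected per condition: 17/3 = 5.667 not closed and 10.333 closed.
- Sum of squared deviations: 2 × (8 − 5.667)² + (1 − 5.667)² = 10.89 + 21.78 = 32.67.
- Chi-square = 32.67/5.667 + 32.67/10.333 = 5.765 + 3.161 = 8.93 on 2 df. p = exp(−8.93/2) = 0.012.
- MLP against KTFS alone: the difference is 0 and p = 1.0.

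**Step 2: the same counts with pairing respected.** The chi-square above ignores that each person contributes to all three conditions. Cochran's Q uses the pairing: Q = (k − 1)[kΣC² − (ΣC)²] / (kΣR − ΣR²), where C are condition totals and R are person totals. With k = 3 the numerator is 2 × (3 × 129 − 17²) = 2 × (387 − 289) = 196. The denominator is 51 − ΣR².

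- Greatest overlap (the same 8 people fail with both devices, one of them also in the third condition): ΣR² = 7 × 4 + 9 = 37, Q = 196/14 = 14.0, p = exp(−7) = 0.0009.
- Least overlap (15 people fail once, one fails twice): ΣR² = 15 + 4 = 19, Q = 196/32 = 6.125, p = exp(−3.06) = 0.047.

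Whatever the overlap, Q is significant at 0.05. Exact McNemar for MLP against KTFS gives p = 1.0, because equal totals force equal discordant counts.

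**Step 3: the overall P value does not separate the patterns.** With 1/16 MLP, 8/16 KTFS and 1/16 third, the expected count is 10/3 = 3.333 and the squared deviations again sum to 32.67. Chi-square = 32.67/3.333 + 32.67/12.667 = 9.80 + 2.58 = 12.38, p = 0.002. A real device difference and no device difference both give a significant three-way result.

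**Step 4: simulation with MLP = KTFS, 16 participants.** First, a within-person permutation test on three labels, set against a paired sign-flip test of MLP against KTFS (1,500 trials; logit-scale person SD 1.0, person-by-condition SD 0.5):

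| Third / each device | Blinks | Three-way rejects | Paired MLP-KTFS rejects |
|---|---|---|---|
| 20% / 20% | 5 | 4.3% | 3.1% |
| 10% / 20% | 1 | 7.9% | not reported |
| 10% / 20% | 5 | 30.8% | 2.9% |
| 10% / 20% | 10 | 52.7% | 3.9% |
| 5% / 20% | 1 | 16.2% | 1.0% |
| 5% / 20% | 5 | 77.4% | 2.9% |
| 5% / 20% | 10 | 95.9% | 4.0% |
| 5% / 30% | 1 | 37.5% | 1.7% |
| 5% / 30% | 5 | 98.3% | 3.7% |
| 5% / 30% | 10 | 99.9% | 3.3% |

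Second, a separate run with other tests and mostly higher device rates (30% to 60%; third condition 5% or 20%; one outcome per person per condition; 20,000 trials). Cochran's Q or Pearson chi-square rejected in 33% to 99.6%, and exact McNemar for MLP against KTFS in 0.5% to 2.1%. With all three rates equal, Q rejected in about 5%. This run supports the direction; with different rates and tests, it does not replicate the table.

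**Step 5: is the contrast supplied elsewhere?** Section 10.4.3 analyses volitional fissure change in mm. The marginal means and intervals promised in Section 10.2 come from the regression for fissure width. Section 10.4.9 names no pairwise test. None gives an MLP-KTFS estimate or interval for the closure probability.

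**The case against.** The strongest reply has four parts.

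- **The wording is open.** Section 10.2 does not say that there is one overall test or that nothing follows it, and Section 10.4.9 also allows for correcting P values, which presupposes several tests. This stands in part: the single-test reading is natural but inferred, as is the identity of the third condition. Even so, no pairwise test is specified, and one added later would be post hoc.
- **The listed question is already answered.** The Protocol Summary's volitional-blink outcome is fissure change, and Section 10.4.3 compares MLP with KTFS on it. This stands. A reader might infer that the plan has no device comparison for volitional blinks; the documents do not support that. The gap is confined to the closure probability.
- **A sham comparison belongs in the design.** The title describes the trial as both sham and active controlled, and Section 7.3.2 gives the sham recording a purpose, to gauge a placebo effect. This stands, so such a comparison need not be dropped or reduced to description.
- **The documents expect a different pattern.** Section 2.1 associates incomplete closure with tape and expects the orbicularis to overcome the magnet. A significant result might then reflect a true device difference. That is possible, but Step 3 shows that the overall P value cannot tell the two patterns apart.

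A reader might also infer an inflated type I error. That does not follow. The test holds its level when all three rates are equal, and the high figures are power against a true difference in the third condition. Harm arises only if that rejection is read as a device difference.

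**Conclusion.** The concern holds in a limited form. Read as one overall test, the closure analysis is valid for its own null but cannot show that MLP and KTFS differ, and a significant result may come solely from a non-randomised third condition. Followed as written, the plan yields no MLP-KTFS test or interval for closure.

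How often this would happen cannot be fixed from the documents. With equal devices and 16 participants, rejection ranged from about 8% to over 99% across the assumed rates and blink counts. It would therefore go too far to say that the three-way test would almost always be significant. The logical point needs none of these rates.

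The conclusion rests on two inferences: that a single overall test is meant, and that the third condition is sham MLP or no device. That it is non-randomised follows directly from there being only two randomised treatments. The point is minor to moderate, and leaves the primary outcome and the listed secondary outcomes untouched.

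**What to change.** In Section 10.2, name the third condition and make a within-person MLP versus KTFS contrast on the probability of incomplete closure, at the 1-week recording, the main closure comparison. Suitable methods are a paired permutation test on each person's proportion, or a logistic mixed model with treatment and period. Report the difference with its 95% confidence interval. Any comparison with sham or no device can stay as a separate secondary comparison, clearly labelled as non-randomised.

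The cost is one sentence of analysis text and no new data. The headline closure result may look less favourable than a three-way P value would.

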10.3 Analysis Datasets

The dataset for the analysis of the primary outcome measure will be an intention-to-treat dataset.

10.4 Description of Statistical Methods

10.4.1 General Approach

This clinical trial uses a prospective, double-masked, within-subjects crossover design. Descriptive statistics for continuous data for each of the primary and secondary endpoints will be presented as means with standard deviations or medians and ranges, as appropriate. The normality of the data will be examined and appropriate statistics and descriptives used based on the results.

Measurements of Eye Lid Kinematics:

Our main measures of device efficacy involves the measurement of eyelid kinematics from video recordings made at various timepoints throughout the clinical trial. **Measurements may be made manually within NIH's image J software, automatically using a software we create (in Python or similar platform), or using crowdsourcing with Amazon Mechanical Turk.**

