10.4.3 Analysis of the Secondary Endpoint(s)

The change in interpalpebral fissure during volitional blinking will be analyzed using the same approach as for the primary outcome measure. Questionnaire responses will be summarized using descriptive statistics and analyzed using non-parametric tests.

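### The normality sentence in section 10.4.1 leaves open whether the mixed model in 10.4.2 governs the interpalpebral fissure (IPF) endpoints

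*Combined protocol and SAP*

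**What the plan says.** Four parts of the combined protocol and SAP bear on this.

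- **10.4.1 General Approach.** One sentence deals with summaries: "Descriptive statistics for continuous data for each of the primary and secondary endpoints will be presented as means with standard deviations or medians and ranges", whichever suits. The next goes further: "The normality of the data will be examined and appropriate statistics and descriptives used based on the results". It does not say which test of normality, at what cutoff, on which quantity (raw IPF, change, paired difference or residual), or what would be used instead.
- **10.4.2, primary endpoint.** "We will use a repeated measures mixed effects model for analysis of the primary outcome measure". The model has a random subject intercept and a fixed treatment effect, and "The model will also include fixed effects of treatment order (i.e., MLP: KTFS vs KTFS:MLP), and crossover period (period 1 or 2"). It also adjusts for age and sham opening IPF. No condition and no fallback are given.
- **10.4.3, secondary endpoints.** Volitional-blink IPF follows the primary approach. For the questionnaires, "Questionnaire responses will be summarized using descriptive statistics and analyzed using non-parametric tests"; that choice is fixed in advance and does not depend on a normality check.
- **10.2 Statistical Hypotheses.** This section also specifies a linear mixed model, but there "the order of interventions (whether evaluated in the first or the second arm of the crossover) will be covariates of interest", and "Effect of each covariate will be investigated alone, and only statistically significant ($P < .05$) covariates will be included in the final regression model".

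Section 10.5 gives the final sample size as 16.

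**The concern.** The sentence on summaries in 10.4.1 already lets the descriptives vary, and 10.4.2 and 10.4.3 already name an analysis for the IPF endpoints and for the questionnaires. The word for statistics in the normality sentence therefore either adds nothing or makes the named IPF analysis conditional on the data. The plan does not say which.

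Three things are at stake:

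- **Pre-specification.** A primary analysis that can be exchanged after a look at its distribution is not fully fixed.
- **Target of the check.** The mixed model relies on roughly normal residuals. Non-normal raw values are not in themselves a reason to abandon it.
- **Estimate.** Section 4.2.1 sets the endpoint as a difference of at least 1 mm. An estimate in millimetres with a confidence interval, adjusted for period, is what answers it. A bare rank-test P value does not.

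**Working it through.** **Sample size.** The 16 in 10.5 cannot be reproduced, because no SD, sidedness or interim effect is given. Assume a two-sided 0.05 level, power 0.80 and a 1 mm difference (10.5 does not say that 1 mm was used). Solving n = ((1.960 + 0.842) × SD / difference)² for n = 16 gives SD = 4 / 2.802 = 1.43 mm for the paired MLP minus KTFS differences. The t-based version gives about 1.33 mm. The power comparison below takes 1.34 mm, at which the period-adjusted analysis has power of about 0.79 to 0.80.

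**How good a gate is the check?** Assume one Shapiro-Wilk test at 0.05 on 16 values. Share of samples rejected:

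- normal data: about 4 to 5% (false alarms)
- gamma shape 4: about 23%
- gamma shape 2: about 42%

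So a test of this size misses most moderate skew. Several independent checks would raise the false-alarm rate: 1 − 0.95² = 0.098 for two and 1 − 0.95⁴ = 0.185 for four. The plan does not say how many would be made.

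**What would the rule cost?** Assumptions, none of them in the documents: 8 per sequence, true difference 1 mm, SD of paired differences 1.34 mm, one Shapiro-Wilk check on the paired differences, and a signed-rank test without period if it rejects. The fixed analysis is a period-adjusted comparison of paired differences, a simple stand-in for the 10.4.2 model. Simulated power:

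| Distribution | Analysis | Period shift 0 mm | 0.5 mm | 1 mm | 1.5 mm |
|---|---|---|---|---|---|
| Normal | fixed | 0.79 | 0.80 | 0.79 | 0.79 |
| Normal | two-stage | 0.79 | 0.79 | 0.78 | 0.78 |
| Gamma 4 | fixed | 0.86 | 0.86 | 0.85 | 0.85 |
| Gamma 4 | two-stage | 0.85 | 0.84 | 0.84 | 0.82 |
| Gamma 2 | fixed | 0.90 | 0.90 | 0.89 | 0.89 |
| Gamma 2 | two-stage | 0.87 | 0.87 | 0.86 | 0.84 |

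The loss is 0 to 1 point with normal data, 1 to 3 with gamma 4 and 3 to 5 with gamma 2. Stronger skew costs more: with exponential data (SD 1.33 mm) and a 1 mm shift, power falls from 0.949 to 0.876, about 7 points.

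**Type I error**, two-stage against fixed, SD 1.33 mm, no period effect in the skewed settings:

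- normal, all settings: 0.044 to 0.054 against 0.045 to 0.054
- gamma 4, 8:8: 0.070 against 0.064, a rise of 0.006
- exponential, 8:8: 0.110 against 0.091, a rise of 0.019
- exponential, 9:7: 0.109 against 0.084, a rise of 0.025, the largest seen

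**If period is left out by any route.** The bias in the treatment difference is the period effect × (n1 − n2)/n. For a 1 mm period effect it is 0 at 8:8, 1 × 2/16 = 0.125 mm at 9:7 and 1 × 4/16 = 0.25 mm at 10:6. Section 10.6.1 aims only at approximate balance on age and on acute versus chronic ptosis, so equal sequence sizes are not assured.

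**The case against.** The strongest reply is that the specific section governs the general one. The normality sentence follows one on descriptives under a general heading, and it names no test or fallback. Sections 10.2 and 10.4.2 both specify a mixed model for the primary outcome. On that reading the sentence concerns summaries only. This is a fair account of the probable intent, and it makes the problem an ambiguity rather than a flat contradiction. It does not remove the ambiguity, because the sentence covers statistics as well as descriptives and no order of precedence is stated.

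Four stronger readings are tempting, and the documents do not support them:

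- *The normality rule drops the period adjustment.* This is an inference. The non-parametric tests in 10.4.3 are for questionnaires, and no section sends IPF to a signed-rank test. A transformation or a robust mixed model would also fit the wording and would keep period. The written route by which period can be lost is the covariate screen in 10.2.
- *Power collapses.* A signed-rank test without period has power of 0.77, 0.71, 0.54 and 0.33 at shifts of 0, 0.5, 1 and 1.5 mm (normal data), but only if it is used in every trial. The rule would use it only after a rejection. Even at the four-check false-alarm rate, the expected loss at a 1 mm shift is about 0.185 × (0.79 − 0.54) = 0.046.
- *The check will fail exactly when a device works.* Section 7.3.2 says "Baseline measures of eye lid blinking without and with the device will be taken during training", and pooled lifted and unlifted lids would look bimodal. But 10.4.1 does not say that they are pooled, and the primary outcome is a change.
- *All endpoints are affected.* The questionnaire tests are already fixed, so the point is confined to the IPF endpoints.

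**Conclusion.** The concern holds as a gap in pre-specification. Section 10.4.1 can be read as making the IPF analysis depend on an undefined normality check, 10.4.2 and 10.4.3 fix that analysis without condition, and the plan does not say which prevails. The check is also a poor one at n = 16 and is not directed at residuals.

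The numerical effect is small: about 0 to 5 power points for normal to moderately skewed data, and a rise in type I error of at most about 0.02 (0.025 in the most extreme setting tried). These figures rest on an assumed Shapiro-Wilk gate, an assumed signed-rank fallback, an SD solved backwards from 16 and 1 mm, equal sequences for the power comparison, and period shifts of 0 to 1.5 mm. Section 10.6.1 supports the possibility of a period shift by noting that acute ptosis may recover during the study, but it gives no size. The more tangible loss, in a trial that did switch to such a test, is the period-adjusted millimetre estimate and its confidence interval.

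The conflict between 10.2 and 10.4.2 over period and order is explicit, and correcting 10.4.1 alone would leave it in place.

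**What to change.** 1. In 10.4.1, limit the normality sentence to the choice of descriptive summary.
2. In 10.4.2 and 10.4.3, state that the mixed model is the analysis for the primary and volitional-blink IPF endpoints whatever a normality check shows, and that model residuals will be inspected.
3. If the residuals look clearly non-normal, add a labelled sensitivity analysis that keeps the crossover structure and does not replace the primary result. One option is a rank-sum or permutation test comparing the period 1 minus period 2 differences between the two sequences. A common period effect cancels in that comparison, and half the Hodges-Lehmann shift between sequences gives a treatment difference in millimetres with an interval.
4. Reconcile 10.2 with 10.4.2: exempt period and order from the P<.05 screen so that both always stay in the model.

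The cost is a few sentences of SAP wording and, if triggered, one sensitivity table. No new data are needed and the sample size of 16 is unaffected.
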